3.3. Result and primary Outcome

Primary Outcome

✓ SARS-CoV-2 infection defined as:

- Detection of SARS-CoV-2 nucleic acid using RT-PCR in any of the specimens collected during the study-follow-up including the asymptomatic participant

-Positive IgG antibodies against SARS-CoV-2 in any of the specimens collected during the study-follow-up

Secondary outcomes

- Serious and non-serious adverse events

- Discontinuation of using the intervention (TDF/FTC or placebo) for any reason

- Adherence to TDF/FTC defined as: number of tablets taken/total number of dispensed tablets

- Severity of SARS-CoV-2 infections according to the following categories:

[figure not shown]
- Asymptomatic infection.

- Mild symptomatic SARS-CoV-2 infection with no need for hospitalization.

- Moderate symptomatic SARS-CoV-2 infection that requires hospitalization, but no ICU.

- Severe SARS-CoV-2 infection: dyspnea with other SARS-CoV-2 symptoms requiring ICU hospitalization.

Graph 1. Flowchart of assignments and follow up of the clinical trial.

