3.1. Study design

Randomized triple-blinded multicentric clinical trial, conducted in parallel, with two arms:

The trial will be performed with health care workers (Physicians, Nurses, Respiratory therapists, or nurse assistants) free of SARS-CoV-2 infection prior, recent or at the time of the inclusion and who directly care for confirmed or suspected cases of COVID-19 in the emergency room, general COVID wards or intensive care units. A screening at baseline will be carried out in order to evaluate for eligibility by performing: SARS-CoV-2 RT-PCR, SARS-CoV-2 IgG antibodies, as well as, hemogram, creatinine, serum phosphorus, AST, ALT, ELISA for HIV, surface Hepatitis B antigen antibodies, qualitative pregnancy test (b-HCG). Once

eligibility is verified participants will be randomly assigned to either an intervention or a control group.

The interventions consists in the administration of Tenofovir/ Emtricitabine (300 mg / 200 mg daily during 60 days) + Personal Protective Equipment (PPE) and the control consists in the administration of placebo (1 tablet daily during 60 days) + Personal Protective Equipment (PPE)

All participants will have PPE recommended for the preventions of COVID-19 by the WHO which include mayo dress, nonfluid long sleeve gown, ocular protection with goggles, face shield or visor and surgical mask in procedures that do not aerosolize. N-95 respirators are required for procedure that generate aerosols. For detailed description see Table 2.

The re-use of N-95 respirators will be allowed according to CDC and WHO guidelines. This taking into consideration the shortage of supplies for the actual situation. The N-95 continuous use will be for 8 hours and the N-95 intermittent use will be allowed up to 5 times with the precaution of storage in a paper and plastic bag label them with the participant name and placed them in a plastic recipient at the end of shifts(48).

After baseline evaluation and confirming eligibility an initial visit and 4 follow up visits at day 20, 40, 60, 75 days will be carried out. See Table 1 and Graph 1.

In the case of presenting COVID-19 related symptoms at any time after enrolling a SARS-CoV2 RT-PCR will be performed between day 1 to 5 of the onset of symptoms and will be repeated it after 72 hours in case that the first one is negative. In the case of having any positive SARS-CoV2 RT-PCR or SARS-CoV2 IgG SARS-CoV2 infection will be confirmed and the intervention will be suspended.

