3.5. Duration of the study and time of termination

- Duration of the interventions: 60 days
- Total duration of the Project: 8 months
 - ✓ 2 months planning, 5 months collecting data, 2.5 months recruiting and a month for data analysis and publication.

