3.6.5. Administration of the intervention product and placebo

Volunteers assigned to the intervention group will receive one tablet of TDF/FTC 300/200mg each day. Each volunteer will be given 60 tablets of the medicine at the beginning of the treatment and its administration will be verified daily by sending a virtual survey, in which the subject answers if he took the intervention, plus a follow-up diary that will be given to the patient of Virtual or manual way for people without access, to write adverse events, as well as the hours of daily exposure to patients with suspected or diagnosed COVID 19 and adherence to personal protection elements. These data will be stored in an eCRF for clinical follow-up, adverse events, and adherence.

Patients assigned to the control group will receive a placebo that will have the same appearance and size and will not have any active ingredients. Similarly, 60 placebos will be delivered from the start of treatment.

The medicine must be stored at a temperature not exceeding 30 ° C and in an environment without excessive humidity in its authorized container and packaging.

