3.6.9. Procedure in case of presenting the primary outcome

If the volunteer, after the start of the study, has a positive result of RT-PCR or IgG for SARS CoV2, which confirms the infection by COVID 19, they will be contacted virtually or in person. During this intervention, the following actions will be carried out:

- You will be given information about your result, and you will be instructed to contact your occupational risk and health insurer.
- The presence of alarm signs (drowsiness, dyspnea, cyanosis) will be evaluated. In case of any of these symptoms are present, the patient will be instructed to attend the emergency service, to receive treatment in accordance with current national and institutional guidelines.
- The volunteer will be instructed to suspend the intervention product, and the masking will be released.
- National Public Health Surveillance System mandatory notification form will be filled out, the institution where the volunteer works will be informed, and the completed form will be sent.

- The volunteer will be informed that telephone follow-up will be carried out every 5 days until the symptoms are resolved or a maximum of six weeks after the diagnosis of COVID 19. In case of presenting any alarm sign during the follow-up, the patient will be recommended to attend the emergency department.

During the telephone follow-up, the volunteer's primary outcome (COVID 19 infection) will be classified as follows: asymptomatic, mild, moderate, or severe COVID. If the patient does not answer due to physical impossibility (e.g. intubation), communication with a companion or family member previously authorized by the patient will be sought.

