The hazard ratio will be estimated by comparing the risk of infection in the intervention group (TDF/FTC + EPP), with the risk in the control group (placebo + EPP), with a confidence interval of 95 %, using a univariate Cox regression model.

If necessary, adjustment will be made for variables that may affect the occurrence of the primary outcome and that are not balanced between the intervention group and the placebo group; The need for adjustment with an OR greater than 1.5 will be considered for dichotomous categorical

variables, such as sex; or if there are differences between the groups greater than 0.25 of the standard deviation for continuous variables such as age, adherence to pharmacological intervention or EPP, and hours of exposure to the COVID area. For the calculation of the adjusted hazard ratio, a multivariate Cox proportional hazards model will be used, if the proportionality assumption is met, or an extended Cox model if this assumption is not met.

For secondary outcomes

-The proportion of incidence of total adverse effects in each group will be determined at day 60 after randomization, estimated as the cumulative incidence using the Kaplan Meier method.

The hazard ratio ("Hazard Ratio") will be estimated by comparing the risk of adverse events in the intervention group (TDF/FTC + EPP), with the risk in the control group (placebo + EPP), with a confidence interval of 95%, using a univariate Cox regression model.

Additionally, the same analysis will be performed for serious adverse events.

- The proportion of incidence of discontinuation of the intervention in each group, for any reason, will be determined at day 60 after randomization, estimated as the cumulative incidence using the Kaplan Meier method.

The hazard ratio will be estimated by comparing the discontinuation of the intervention in the intervention group (TDF/FTC + EPP), with the risk in the control group (placebo + EPP), with a confidence interval of 95 %, using a univariate Cox regression model.

- It will be determined as the difference in the mean or median (according to the distribution of the data) of the percentage in which the individuals were adherent

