Nausea	Qualitative/nominal	A feeling of sickness featured by an urge to vomit.	1-Grade 1 2-Grade 2 3-Grade 3
Headache	Qualitative/nominal	Headache	1-Grade 1 2-Grade 2 3-Grade 3
Abdominal pain	Qualitative/Nominal	A feeling of distress or pain in abdominal area.	1-Grade 1 2-Grade 2 3-Grade 3
Flatulence	Qualitative/nominal	A disorder highlighted by abnormally increased gas discharge by lower gastrointestinal tract.	1-Grade 1 2-Grade 2
Insomnia	Qualitative/nominal	A disorder characterized by difficulty to start or maintain sleep.	1-Grade 1 2-Grade 2 3-Grade 3
Vomit	Qualitative/nominal	A disorder featured by a reflex act or actively regurgitating stomach contents through mouth	1-Grade 1 2-Grade 2 3-Grade 3 4-Grade 4 5-Grade 5
Maculopapular skin rash	Qualitative/nominal	A disorder featured by the appearance of macules and papules. Also known as morbilliform eruption. Often associated with pruritus.	1-Grade 1 2-Grade 2 3-Grade 3
Steven-Johnson's syndrome	Qualitative/nominal	A disease in which at least 10% of body surface area develops a severe sphenelating lesions and bullae, also compromising mucosal membranes.	3-Grade 3 4-Grade 4 5-Grade 5
Allergic reaction	Qualitative/nominal	A disorder featured by a local or diffuse skin reaction upon exposure to an allergenic.	1-Grade 1 2-Grade 2 3-Grade 3 4-Grade 4 5-Grade 5
Other allergic reaction	Qualitative/nominal	Se coloca la clasificación de la reacción alérgica reportada según la	1-Grade 1 2-Grade 2 3-Grade 3 4-Grade 4 5-Grade 5
Adherence by tablet count	Qualitative/discrete	Number of drug/placebo tablets taken to follow-up date	Number of tablets
Drug/placebo interruption	Qualitative/dichotomous	Any interruption of investigational product	0- No 1- Yes
Days of product interruption	Quantitative/discrete	Days of drug interruption	Number of days
Cause of drug interruption	Qualitative/nominal	Reason of drug interruption	1- Omission 2- AE 3- Accidental los of drug/placebo 4- Non-availability of drug/placebo
Additional data to be collected in Follow-up 2 and 3			

Temperature	Quantitative/continuous	Body temperature in Celsius degrees	Temperature in Celsius degrees
Heart rate	Quantitative/discrete	Heart rate	Heart rate in beats per minute
Respiratory rate	Quantitative/discrete	Respiratory rate	Respiratory rate in respirations per minute
Systolic blood pressure	Quantitative/discrete	Systolic blood pressure	Systolic blood pressure in mmHg

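### Adherence is divided by all 60 dispensed tablets, so participants who comply until an instructed early stop score low, and adherence is mixed with discontinuation

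*Combined protocol and SAP*

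**What the plan says.** - **Definition.** Section 3.3 lists adherence as a secondary outcome: "number of tablets taken/total number of dispensed tablets".
- **Denominator.** Section 3.6.5 states for the active arm that "Each volunteer will be given 60 tablets of the medicine at the beginning of the treatment", and for placebo "Similarly, 60 placebos will be delivered from the start of treatment". Section 3.5 gives "Duration of the interventions: 60 days". The denominator is therefore 60 for everyone.
- **Instructed stops.** Under section 3.1, after any positive RT-PCR or IgG, "infection will be confirmed and the intervention will be suspended". The section 3.6.9 procedure for the primary outcome repeats this. The withdrawal criteria (also numbered 3.6.9) add kidney abnormalities, the need for an interacting drug, and related serious adverse events.
- **Analysis.** Section 4, under secondary outcomes, compares the arms by the "difference in the mean or median (according to the distribution of the data) of the percentage in which the individuals were adherent". It gives no rule for instructed stops, and no test or confidence interval for this outcome.
- **Data.** Appendix 3 records adherence as "Number of drug/placebo tablets taken to follow-up date". That is a numerator only and supplies no other denominator.
- **Second use.** Section 4 also names adherence as a possible adjustment covariate for the primary Cox model if the arms differ by more than 0.25 SD.

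**The concern.** The measure should show how well participants took the tablets they were meant to take. With the denominator fixed at 60, it also counts tablets the protocol told them not to take. Three things follow.

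1. A fully compliant participant receives a low score.
2. One infection stop lowers adherence and also counts as a discontinuation, which is a separate secondary outcome.
3. The plan expects twice as many infections on placebo, so the arms can differ in mean adherence when tablet-taking behaviour is the same.

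The covariate use adds a further problem: infection lowers the score, so adjusting for it would put a consequence of the event into the model for that event.

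**Working it through.** **The plan's own figures.** The documents give no adherence figure. The infection risks used below come from section 3.4, which states 429 per arm for 0.10 against 0.05. The pooled two-sided formula gives [1.96 × √(2 × 0.075 × 0.925) + 0.8416 × √(0.09 + 0.0475)]² / 0.05² = 434.4, so 435 per arm. The stated figure is within 3% of that. Sample size is not affected by this point.

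**One participant.** If every tablet is taken until an instructed stop, the score is stop day / 60: 33% at day 20, 50% at day 30, 67% at day 40.

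**Arm means.** Let a be true adherence while on product, p the infection risk, f the share of infections that stop product before day 60, and L the mean share of the 60 tablets forgone. Only p comes from the plan; a, f and L are assumptions.

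Arm mean = a × (1 − p × f × L), so gap = a × f × L × (0.10 − 0.05).

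- a = 1, f = 1, L = 0.5 (stops uniform over 60 days): placebo 95.0%, active 97.5%, gap 2.5 points.
- a = 0.80 to 0.92, same f and L: gap 2.0 to 2.3 points.
- f = 0.5, L = 0.5, a = 0.80 to 1: gap 1.0 to 1.25 points.
- All stops at day 40 (L = 1/3), f = 1, a = 0.80 to 1: gap 1.3 to 1.7 points.
- Ceiling, all stops at day 0 with a = 1: 5 points.

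**A version tied to the testing schedule.** Assume infections uniform over 75 days and a = 0.94. Symptomatic cases stop d days after infection, where d = 6.5 to 11.5 (the 5.5-day mean incubation in section 1.3 plus 1 to 6 days for swab and result). Asymptomatic cases are caught early only by the day-40 IgG, if infected at least 14 days before. The asymptomatic share is 18% to 46.5% (section 1.3).

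- Symptomatic, mean share forgone = (60 − d)² / (2 × 60 × 75): 0.318 at d = 6.5, 0.261 at d = 11.5.
- Asymptomatic: (26/75) × (20/60) = 0.116.
- High end: 0.94 × 0.05 × (0.82 × 0.318 + 0.18 × 0.116) = 1.3 points.
- Low end: 0.94 × 0.05 × (0.535 × 0.261 + 0.465 × 0.116) = 0.9 points.

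**Simulation.** 475 per arm, 1,000 replicates, equal true adherence, risks 0.10 and 0.05, stop times uniform. The last column applies a two-sided 5% t-test, which the plan does not specify.

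| True adherence (assumed) | f | Mean gap | Median gap | Standardised gap | Beyond 0.25 SD | t-test rejects |
|---|---|---|---|---|---|---|
| Perfect | 1 | 2.5 | 0.0 | 0.17 | 9% | 73% |
| Perfect | 0.5 | 1.2 | 0.0 | 0.11 | 1% | 44% |
| Mean 0.92, SD 0.06 | 1 | 2.3 | 0.4 | 0.15 | 4% | 63% |
| Mean 0.92, SD 0.06 | 0.5 | 1.1 | 0.1 | 0.09 | 1% | 29% |
| Mean 0.90, SD 0.10 | 1 | 2.2 | 0.8 | 0.13 | 3% | 53% |
| Mean 0.90, SD 0.10 | 0.5 | 1.1 | 0.3 | 0.07 | 1% | 21% |
| Mean 0.80, SD 0.20 | 1 | 2.1 | 1.5 | 0.09 | 1% | 30% |
| Mean 0.80, SD 0.20 | 0.5 | 1.0 | 0.7 | 0.04 | 0% | 10% |

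With risk 0.10 in both arms (no drug effect; mean 0.90, SD 0.10, f = 1) the mean gap is 0.02 points.

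**After the fix.** Dividing by tablets due up to the instructed stop gives mean gaps of −0.09 to +0.05 points in the eight scenarios above, with 0 to 5% of t-tests rejecting.

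**The case against.** The strongest reply is that tablets taken over tablets dispensed is a legitimate measure of overall product use. Discontinuation is reported separately with its own hazard ratio, so a reader can tell the two apart, and the primary estimate is an unadjusted Cox model that this definition does not touch. The primary estimate is indeed untouched. But the stated objective is adherence, and a score of 50% for someone who followed every instruction does not measure it.

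Several objections limit the size and certainty, and they stand:

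- The plan chooses mean or median by distribution. Adherence near a 100% ceiling is skewed, and the median barely moves.
- Infections first found at day 60 or 75 cost no tablets, and a day-40 finding costs at most a third.
- Withdrawal stops may run the other way. For example, an excess of 3 percentage points of active-arm participants stopped at day 40 would cost 0.03 × 1/3 = 1 point, enough to cancel the lower end of the range. Section 5.1.1 reports, for a cited HIV prophylaxis trial, six creatinine discontinuations on tenofovir-containing arms and none on placebo. That suggests a direction but does not size it for this trial.

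A reader might infer that stopped participants are classed as non-adherent. The documents set no cut-off; these participants simply receive a lower percentage. A reader might also take the rejection rates as the chance of a false claim in this trial. Section 4 names no test for adherence, so those rates are illustrative only.

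**Conclusion.** The definition mis-scores participants who comply until an instructed stop, and it mixes adherence with discontinuation. Both follow from the text without assumptions.

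The between-arm consequence is conditional and small: roughly 1 to 2.5 points on the mean, lower on placebo. It assumes infection risks of 0.10 and 0.05, equal true adherence, and the stop times and early-detection shares set out above. It is about zero if the drug does not work. The documents do not support the stronger inference that the trial will show better adherence on active drug, because other instructed stops could offset or reverse the gap.

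As a covariate, the variable is partly determined by the primary outcome. This gap alone would rarely trigger adjustment (at most 9% of simulated trials), so the covariate problem is one of principle more than of likely effect. The point is minor but worth correcting.

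**What to change.** In section 3.3 and section 4, define adherence as tablets taken divided by tablets due from first dose to the earlier of day 60 or the date product was stopped on protocol instruction. Use this for the between-arm comparison, and report early stops under the discontinuation outcome. State which stops count as instructed: infection and withdrawal codes 1 to 3 in Appendix 3 (kidney, interacting drug, related serious event) would, while stops by the participant's own decision (codes 4 and 5) would not shorten the denominator.

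The cost is a definition line plus one added reason code, SARS-CoV-2 infection, in the Appendix 3 withdrawal variable. The code is needed because the present reasons omit infection and the stop date is recorded only when a reason is coded. The positive RT-PCR date is collected, but it is not a product stop date. No visit, laboratory test or sample-size change follows.

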3.4. Sample size

An estimative of the number of required participants was done according to the following parameters:

- Risk of SARS-CoV-2 infection reported in the world: despite of the little data available on incidence reports from China, The Netherlands and Madrid vary from 6 to 38.9 per 100 exposed health care workers. The high variability on the incidence is related to the develop of institutional outbreaks, thus establishing a latent risk in all hospital institutions in a pandemic scenario (7,44,76). To assess the sampling size calculation for this study, besides what has been reported internationally, an approximate calculation of the incidence of SARS-CoV-2 infection in the health care institutions in which the study will be held was performed. It is important to know the infection and epidemic control variates from one institution to another. While some actively screen asymptomatic health care personnel others only screen symptomatic health care personnel. The incidence observed in a 2-month period of time variates between 3.3% and 13.7% with a mean of 11.2 cases per 100 health care workers.

Based on that preliminary information, an expected risk for SARS-CoV-2 infection in the control group (Placebo + PPE) of 0.10 was used for the calculation. With the objective of estimating precisely a 50% relative risk reduction an assumption of an expected risk of 0.05 was done in the intervention group (Tenofovir/Emtricitabine + PPE) in order for a difference of 0.05 to detect between both groups.

- Power: 0,80. Alfa level: 0.05
- Assigantion ratio $n_1/n_2 = 1:1$ (randomization1: 1).
- Sample size: 858 (429 per group).

Considering possible loses up to 10% it is risen to 950 in total (with randomization 475 participants to each group).

As a limitation of the study, if the incidence or the effect of the interventions are considerably lower than expected, the power to detect significant differences between both groups will be reduce. However, due to the progression of the pandemic in our country, with a tendency to increase, it is probable that the incidence observed in health care professionals will remain stable or even increase not only for the intrahospital risk, but for the risk in the community,

3.5. Duration of the study and time of termination

- Duration of the interventions: 60 days
- Total duration of the Project: 8 months
 - ✓ 2 months planning, 5 months collecting data, 2.5 months recruiting and a month for data analysis and publication.

3.6. Procedures

In table 1. Detailed follow up evaluations are described.

Table 1. Description of the evaluations to be done during the trial.

Follow up table				
Day	General activity	Specific activity	Responsible	Result
0	Base line diagnoses	Initial Clinical evaluation	Medical doctor of the study	Evaluating inclusion and exclusion criteria. Signing informed consent form
		Blood samples	Nurse Lab tech	Laboratory report: hemogram, creatinine, phosphorus, AST, ALT HIV ELISA, HB Surface antigen antibodies
		SARS-CoV-2 RT-PCR sampling	Respiratory therapist or nurse	Result of SARS-CoV-2 RT-PCR
		SARS-CoV-2 IgM and IgG antibodies	Nurse Lab tech	Result of IgM and IgG antibodies
		b-HCG sampling in women	Nurse Lab tech	Report of b-HCG
20	Visit 1	Clinical evaluation	Medical doctor of the study	Clinical record and eCRF for clinical evaluation, adherence, and adverse events

40	Visit 2	Blood sample for: SARS-CoV2 IgM, IgG antibodies and blood chemistry	Nurse Lab tech	Laboratory report of SARS-CoV2 IgM, IgG antibodies and creatinine
		Clinical evaluation	Medical doctor of the study	Clinical record and eCRF for clinical evaluation, adherence, and adverse events
60	Visit 3	Blood samples	Nurse Lab tech	hemogram, creatinine, phosphorus, AST, ALT HIV ELISA, HB Surface antigen antibodies b- HCG in women
		SARS-CoV-2 RT-PCR sampling	Respiratory therapist	Result of SARS-CoV-2 RT-PCR
		Clinical evaluation	Medical doctor of the study	Clinical record and eCRF for clinical evaluation, adherence, and adverse events
75	Visit 4	Blood samples	Nurse Lab tech	Laboratory report of SARS-CoV2 IgG
		Clinical evaluation	Medical doctor of the study	Clinical record and eCRF for clinical evaluation,
		End of follow up and communication to study subject	Clinical coordinator	Minutes

During follow up to any participant who develop COVID-19 related symptoms at any time after randomization given by two or more of the following: Body temperature higher than 38 Celsius, cough of recent onset (in the previous 10 days), dyspnea,odynophagia, malaise, fatigue, acute diarrheal disease, ageusia, dysgeusia, anosmia or hyposmia, an RT-PCR will be performed within the next 5 days and will be repeat it if the result is negative and the symptoms persist. This RT-PCR will be performed at every of the centers of the study and will request the patient the immediate report of the symptoms through an app or via phone call. In case of a positive RT-PCR the infection

will be confirmed. While confirmation RT-PCR arrives, the participant will not quit taking the intervention. In that scenario, the intervention will only be suspended in the case of a highly suspected case or severe case requiring hospitalization.

In case the infection is ruled out in the follow up, the participant will continue the interventions and follow up scheduled, according to graph 1.

With regards to diagnostic testing during follow up as shown in table 1. IgG antibodies will be done at visit 2 and 4 (40 days from initially taking the intervention and 15 day after finalizing it). This considering volunteer that might acquire the infection in the last days of the pharmacological intervention. Moreover, at day 60, last of the intervention, an RT-PCR will be performed to all participants. This in order to detect participants who develop asymptomatic infection. The research group is aware that this follow up will not identify a 100% of the asymptomatic infection for the low sensitivity of testing in this scenario, approximately 30 to 40% (46,47), yet it will be done in both arms.

Importantly, for the covid-19 emergency, clinical follow up, adverse event reporting and adherence reporting could be done online.

Personal Protective Equipment

All volunteers will be using the following personal protective equipment. This based on the guidelines of the WHO (23). See table 2.

Table 2. Use of PPE by study volunteers.

Area	Health care personnel or patients	Activity	Type of PPE or activity
Emergency room, general COVID wards or intensive care units	Health care workers	Direct contact with the patient of non-aerosol generating procedures.	Surgical mask Visor or glasses. Long sleeve gown Nonsterile gloves.
		Direct contact with the patient and aerosol generating procedures.	N95 respirator Visor or glasses. Long sleeve gown Nonsterile gloves. May dress

			under the robe that is removed at the end of the shift
Other areas of transit (hallways or waiting rooms)	All personnel including health care workers	Any activity that does not involve contact shorter than 2 meters in distance between people	Surgical mask

Adapted from: Rational use of personal protective equipment for coronavirus disease 2019 (COVID-19). Interim guidance 27 February 2020. World Health Organization. (23)

*Health care worker: person in whose activity directly care a contact, suspected, or confirmed case of COVID-19.

